LIBERATE – LIquid Biopsy Evaluation and Repository Development AT PrincEss Margaret
LFS – Li-Fraumeni Syndrome
Lynch/LS – Lynch Syndrome
MOHCCN - Marathon of Hope Cancer Centre Network
MTA - Material Transfer Agreement
MRN - Medical Record Number
NF1 – Neurofibromatosis Type 1
NPV - Negative Predictive Value
OICR - Ontario Institute for Cancer Research
PHI - Personal Health Information
PPV - Positive Predictive Value
SOP – Standard Operating Procedure
sWGS – Shallow Whole Genome Sequencing
TIDHI - Toronto Immune Digestive Health Institute
TP – Targeted Panel

Protocol Summary

CfDNA in Hereditary And High-risk Malignancies (CHARM) 2: Evaluating the Performance of a cfDNA Blood Test for Early Cancer Detection

Randomized Control Study

Sample Size

Total = 1000 patients with Hereditary Cancer Syndromes (HCS)

N = 500 (experimental arm)

N = 500 (control arm)

If other sites join our study, the appropriate MTAs and DTAs will be established, and samples collected at other institutions (who have institutional REB approval for the study) will be sent to UHN/OICR for analysis. Other sites may include: BC Cancer Agency, Mount Sinai Hospital, SickKids Hospital, Women's College Hospital, Sunnybrook Hospital, McGill Research Institute, Jewish General Hospital, IWK Health Centre, Eastern Health, Alberta University.

We will recruit up to 1000 patients at UHN.

Study Population

Our study focuses on patients with a known Hereditary Cancer Syndrome (HCS).

Accrual Period

January 2024 – December 2024

Study Design

Through the CHARM Consortium (www.charmconsortium.ca), we have shown that cell-free DNA (cfDNA) profiling can enable more frequent cancer surveillance from readily accessible blood collections and can detect cancer at the same time or earlier than clinical screening approaches. We are now conducting a prospective, multi-center, randomized control trial of cfDNA testing of 1,000 HCS carriers to 1) compare cancer detection rates with and without cfDNA testing, 2) assess cancer stage shift and clinical impact reducing mortality and morbidity cancers, and 3) assess impact of access to cfDNA results on patients' quality of life and psychological distress.

Study Duration

January 2024 – December 2031

Study Agent/ Intervention/ Procedure

cfDNA sequencing (on a blood sample), tri-annually for 4 years.

Primary Objective

Decrease the time to cancer detection and disease management in HCS carriers receiving cfDNA sequencing results compared to controls.

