2.0 Background Information

2.1 Background and Rationale

Early cancer detection is the surest path to survival, even cure. As cancer progresses, genetic changes continue to amass, thereby making late-stage cancers more aggressive, harder to eradicate, and more lethal. People who are affected by a hereditary cancer syndrome (HCS) have this lived experience, as they are born with a genetic change that puts them at high risk for developing multiple cancers throughout their lifetime. Over 200,000 Canadians harbor mutations in one of the >100 genes that cause an HCS, some facing a 100% lifetime risk of developing cancer^{1,2}. To find these cancers in time for effective treatment, all of these carriers undergo highly specific medical imaging and physical exams on a biannual or annual basis, often travelling 100s of kilometers at significant personal stress, expense, and time investment. Sadly, many of these patients receive late-stage cancer diagnoses, necessitating immediate and often radical surgeries, radiation treatments, or enrollment in experimental clinical trials.

People who carry an HCS genetic variant describe themselves as “ticking cancer time bombs” as they await the accumulation of mutations during their lifetime that trigger cancer development³. Depending on cancer type, individuals may be able to enroll in publicly-funded annual surveillance programs that are cancer-type specific and entail an array of comprehensive clinical exams and imaging modalities, such as full-body MRI, colonoscopies and mammograms. In HCS that predispose cancers for which early detection has not yet been possible, prophylactic surgeries are recommended, such as removal of breasts, ovaries, and fallopian tubes for carriers of Hereditary Breast and Ovarian Cancer (HBOC), removal of uterus and ovaries in Lynch Syndrome (LS), and gastrectomy for carriers of Hereditary Diffuse Gastric Cancer (HDGC)^{4,5,6}. These life-altering surgeries place a heavy psychological and physical burden on patients, particularly those of childbearing age who face uncertain timing of growing a family versus potential development of a cancer.

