4.1 Overall Study Design

We are conducting a randomized control trial to assess the use of cfDNA analysis in cancer surveillance protocols for patients with HCS. We will recruit 1,000 patients across Canada with a known/suspected genetic diagnosis of one of the following HCS: HBOC, LS, NF1, LFS, PALB2, or HDGC that are receiving standard-of-care clinical assessment for cancer by a managing physician under a provincial screening program or cancer surveillance protocol.

The study design is illustrated in Figure 1. At study enrollment, participants will be randomized to a control cohort (n=500) or an experimental cohort (n=500), stratifying for genetic HCS background. All participants in the experimental cohort will provide blood samples tri-annually (every four months) for four years, either at the study hospital, or at a local blood laboratory (e.g., LifeLabs or Dynacare). Whenever possible, patients will have research blood collected at the same time as routine blood collections for clinical purposes, to avoid additional venipunctures. Participants randomized to the control cohort will have the option to donate samples to the CHARM Consortium Biobank, for use in future research. Participants in the control cohort can donate between 1-3 blood samples a year, for the duration of the study.

Participants in both the control and experimental cohorts will continue to receive standard-of-care cancer surveillance according to current guidelines, as they were prior to study enrollment. Blood samples from the experimental cohort will be subject to a

Figure 1. Study Design.

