8.0 Statistics

We will compare the cancer detection rate between control and experimental cohorts. Analysis will be stratified by the type of the tumours detected within each HCS, as well as across the entire cohort. Between the cohorts, we will first compare the cancers detected to ascertain whether cfDNA testing results in a more sensitive detection of clinically confirmed cancers, as well as calculate negative and positive predictive values of cfDNA findings as confirmed by clinical testing (MRI, ultrasound, biopsy, protein biomarkers, etc.). This analysis will also ascertain whether cfDNA is more or less effective at detecting specific cancer types compared to standard-of-care screening alone.

We will also conduct comparisons that compare categorical (e.g. cancer stage) and continuous time course data (e.g. time to symptom development, time to treatment, and time on treatment). The first comparison is a stage shift analysis, whereby we will assess whether cancers are being detected at earlier stages using cfDNA versus screening results from the same programs. Categorical variables of stages I-IV within each cancer type as defined by NCCN criteria will be compared using Pearson's χ^2 test. Binary comparison of “early” and “late” stage across all cancer types will be performed using Fisher Exact test. The second comparison will be calculation of the time to first treatment relative to the date of the last annual clinical screening visit. This comparison of continuous variables using the t-test will establish whether triannual cfDNA testing accelerates off-cycle clinical follow-up and medical treatment compared to waiting for annual clinic visits. The third comparison will compare mortality and morbidity specifically for pancreas, esophagus, brain, lung, and stomach cancers. We will calculate the time between detection of a cancer and when patient manifest symptoms of cancer (morbidity 1), how long patients are afflicted with cancer symptoms after detection and during treatment (morbidity 2), and how long a patient undergoes treatment before succumbing to disease (mortality) or, in the case of effective treatments, the time until treatment is discontinued, or patients transition to the outpatient setting. Continuous variables will be compared by t-test.

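### Morbidity 1 starts its clock at detection, so its between-arm t-test measures lead time and not reduced morbidity; the mortality variable shares the bias only in part

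*Protocol*

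**What the plan says.** The Protocol Summary (Study Design) gives the trial's second aim as to "assess cancer stage shift and clinical impact reducing mortality and morbidity cancers". Section 8.0 serves that aim with three comparisons, of which the last is this: "The third comparison will compare mortality and morbidity specifically for pancreas, esophagus, brain, lung, and stomach cancers".

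Three durations are defined for it:

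- Morbidity 1: "We will calculate the time between detection of a cancer and when patient manifest symptoms of cancer (morbidity 1").
- Morbidity 2: "how long patients are afflicted with cancer symptoms after detection and during treatment (morbidity 2").
- Mortality: "how long a patient undergoes treatment before succumbing to disease (mortality"). Where treatment works, the end is instead stopping treatment or moving to outpatient care.

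The test is fixed in the same place: "Continuous variables will be compared by t-test".

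On timing, Section 4.1 says: "All participants in the experimental cohort will provide blood samples tri-annually (every four months) for four years". Section 2.1 describes existing surveillance as "highly specific medical imaging and physical exams on a biannual or annual basis". The primary objective (Section 3.1.1) and the potential benefits (Section 4.13.2) both present earlier detection as what the test may bring. The Protocol contains no symptom or mortality analysis that starts at randomisation, no lead-time correction and no caution about lead time.

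**The concern.** A duration can be compared fairly between randomised arms only if its starting point does not depend on the arm. Morbidity 1 starts at detection, which the intervention is built to move. A longer detection-to-symptom interval in the cfDNA arm is therefore expected even if every patient develops symptoms on the day they would have done anyway.

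The label matters. The variable is called morbidity, it sits in a comparison of mortality and morbidity, and it answers an aim about reducing both. A significant difference would naturally be reported as a gain in symptom-free time. A test that only advanced the date of diagnosis could be credited with a clinical benefit that no patient received.

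**Working it through.** **Step 1: algebra, no assumed numbers.** For a given cancer let S be the date of first symptoms, D the date of death, T the detection date under standard surveillance, and L the lead time, so that cfDNA detection falls at T - L. Suppose cfDNA changes neither S nor D.

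- Morbidity 1: control S - T; cfDNA S - (T - L) = (S - T) + L. The difference is exactly L.
- Mortality: if treatment starts at detection and runs until death, control D - T; cfDNA (D - T) + L. The difference is again L, but only under that condition.
- Morbidity 2: if detection comes no later than symptoms, the symptomatic period runs from S onward in both arms, and L does not enter. If detection comes after symptoms, the part before detection is not counted, so the variable still depends on the detection date, but not as an added lead time.

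Averaged over cancers, the error in morbidity 1 is the mean lead time, whatever the sample size.

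**Step 2: effect on the t-test.** The Protocol gives no lead time, SD or case count for the five cancer types. Assumed: mean lead time L of 3 to 6 months across the cfDNA arm's cancers (about one draw interval), SD of 10 to 15 months, and 3 v 6, 5 v 10 or 7 v 15 cases (control v cfDNA). With no true benefit, the t statistic is noncentral with df = n1 + n2 - 2 and

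noncentrality = (L / SD) / sqrt(1/n1 + 1/n2).

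Examples:

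- 7 v 15: sqrt(1/7 + 1/15) = 0.458. L = 3, SD = 15 gives 0.2/0.458 = 0.44. L = 6, SD = 10 gives 0.6/0.458 = 1.31.
- 3 v 6: sqrt(1/3 + 1/6) = 0.707. The same two settings give 0.28 and 0.85.

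Two-sided rejection rate at nominal 5%:

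| Cases | L 3, SD 15 | L 4, SD 10 | L 5, SD 10 | L 6, SD 10 |
|---|---|---|---|---|
| 3 v 6 | 5.7% | 7.8% | 9.4% | 11.4% |
| 5 v 10 | 6.3% | 10.4% | 13.5% | 17.4% |
| 7 v 15 | 7.0% | 13.2% | 18.0% | 23.9% |

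These are two-sided rates, against a baseline of 5%. Counting only rejections that favour cfDNA, the baseline is 2.5% and the corner values are 4.3% (3 v 6, L 3, SD 15) and 23.8% (7 v 15, L 6, SD 10).

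**Step 3: simulation with no benefit.** Symptom and death dates had the same distribution in both arms. Testing was every 12 months (control) or every 4 months (cfDNA). Assumed: 50% sensitivity per test, exponential preclinical period with mean 6, 12 or 24 months, mean 12 months from symptoms to death, treatment from detection until death. A cancer found only through symptoms counted as zero for morbidity 1. The cfDNA arm's continuing standard screening was not added.

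| Mean preclinical period | Detection to symptoms, control v cfDNA | Treatment to death, control v cfDNA | False gain |
|---|---|---|---|
| 6 months | 1.4 v 3.0 | 13.4 v 15.0 | 1.6 |
| 12 months | 4.7 v 8.0 | 16.7 v 20.0 | 3.3 |
| 24 months | 13.6 v 19.2 | 25.6 v 31.2 | 5.6 |

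At 10 cancers per arm the t-test rejected in 9-11% of runs for morbidity 1 and 5-8% for mortality. Symptom duration was unchanged (12.0 v 12.0 months). Time to death from an origin common to both arms was also equal (18.0 v 18.0, 24.0 v 24.0 and 36.0 v 36.0 months), with rejection at about 4-6%. The simulation's common origin was onset of detectability; in the trial, the arm-independent origin available is randomisation.

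**The case against.** Four points can fairly be made in the plan's defence.

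- **The mortality variable is not survival from diagnosis.** A reader might infer that survival is inflated by the full lead time. The text does not support that. The variable is time on treatment until death, and a cancer found early and treated with a short course could give a shorter value. This stands: for mortality the bias is conditional.
- **Morbidity 2 is different.** A reader might take all three clocks to be biased alike. Lead time does not lengthen morbidity 2 in this way. This stands too.
- **The case counts are small.** It is tempting to use 25 v 50 cases, since Section 8.0 speaks of detection rates of 5% and 10%, and 500 x 5% = 25 and 500 x 10% = 50. Those are cancers of every type. The comparison covers only five, in a population that includes hereditary breast and ovarian cancer and Lynch syndrome, so those counts do not apply. At 3 v 6 cases the rejection rate is 6-11%, not far above nominal. This limits false significance but leaves the bias in the estimate untouched.
- **This is a supporting comparison, and a separate analysis plan may exist.** It is not the powered outcome, nor one of the four endpoints in Section 4.11. That lowers the severity. It does not remove the point, because Section 8.0 itself fixes the start, the end and the test for morbidity 1, and the Protocol Summary names mortality and morbidity in the trial's second aim.

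**Conclusion.** The point holds for morbidity 1 without any assumed figure: with no symptom postponed, the interval is longer in the cfDNA arm by the mean lead time, so its t-test cannot show reduced morbidity. For mortality it holds to the extent that treatment begins soon after detection and continues to death. It does not extend to morbidity 2.

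The rise in the two-sided rejection rate to about 6-24% rests on the assumed lead times, SDs and case counts and would change with them. The direction, and the equality of the morbidity 1 bias with the mean lead time, would not. This should be fixed, but it does not threaten the trial's powered comparison.

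**What to change.** In Section 8.0, replace the tested part of the third comparison with two outcomes measured from randomisation in all randomised participants, by arm as assigned:

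- time to first symptomatic cancer of the five named types;
- time to death from one of those cancers.

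Use time-to-event methods, censor at withdrawal or end of follow-up, and treat other deaths as competing events. Keep the detection-to-symptom and time-on-treatment intervals as descriptive figures, labelled as including lead time, with no test.

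**Cost.** No extra patients or visits: Section 4.8 (Collection of Clinical Data) already plans clinical data for up to 7 years from enrolment. It is more than a wording change, though. Dates of symptom onset and death must be recorded; the list in Section 4.8 names neither explicitly, although the existing comparison already needs them. Section 5.3 stops data collection at withdrawal, so withdrawn participants contribute only up to that date. Events will be few and precision low, and the result will probably look less favourable to cfDNA than the present analysis would.

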Power analysis is based on the primary outcome of improved cancer detection at various diagnosis rate scenarios of the study cohort at the end of the study, range with current 5% detection rate for all HCS without cfDNA modeling, up to 10% should cfDNA improve

detection. Based on the power analysis, our study with 1,000 patients will achieve >97% statistical power to detect at least 2% increased diagnosis rate attributable to cfDNA testing with 2-sided significance level at 0.05.

Lastly, analysis of the survey data will be led by [name] at Unity Health and [name] at Memorial University. DTAs will be established and signed by all institutions, prior to sharing of any data. Baseline adjusted mean differences between groups with 95% confidence intervals will be calculated for test-specific distress and uncertainty, generalized distress, anxiety, empowerment and quality of life; a regression framework for hypothesis-generating purposes will be used. Estimates of variance and correlation among emotional outcomes and empowerment, and quality of life and between groups will be determined. Proportion of cases and drop outs from rural/remote geographic regions across arms will be compared using a chi square test. P-values are set at 0.05 (two-tailed).

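### The claimed >97% power for a 2-point gain in diagnosis rate does not follow from the protocol's inputs: 500 per arm gives about 27% at 5% vs 7%, and about 85% at 5% vs 10%

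*Protocol*

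**What the plan says.** The power statement is in Protocol section 8.0. It names cancer detection as the primary outcome and takes the diagnosis rates at study end. It gives those rates as: "range with current 5% detection rate for all HCS without cfDNA modeling, up to 10% should cfDNA improve". It then concludes that "our study with 1,000 patients will achieve >97% statistical power to detect at least 2% increased diagnosis rate attributable to cfDNA testing", using a two-sided 0.05 level. It names no test, shows none of the scenarios it mentions, and makes no allowance for loss.

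The comparison is between the randomised arms. Section 8.0 opens with "We will compare the cancer detection rate between control and experimental cohorts", and section 4.1 says that "participants will be randomized to a control cohort (n=500) or an experimental cohort (n=500), stratifying for genetic HCS background". The Protocol Summary gives the same 500 and 500.

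**The concern.** With 500 per arm, a 5% rate means about 25 cancers in the control arm and a 7% rate about 35 in the experimental arm. A difference of 10 events between two counts of that size is well within chance variation, so near-certain detection is implausible on its face.

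This sentence is the only sample-size justification in the protocol. If the real gain is 2 points, a design said to miss it less than 3% of the time would miss it about 73% of the time. Anyone who relied on the stated power when reading a non-significant result would draw far too firm a conclusion. The ethics board and the funders are also judging the trial's ability to answer its question on this figure.

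**Working it through.** **Inputs (all from the protocol)**
- n = 500 per arm (Protocol Summary; section 4.1).
- Control rate p1 = 0.05 and experimental rate p2 up to 0.10, at the end of the study (section 8.0).
- Smallest effect claimed as detectable: 2 points, so p2 = 0.07 (section 8.0).
- Two-sided alpha 0.05, so z = 1.96 (section 8.0).
- Assumption: no loss. Section 5.3 allows withdrawn participants to be replaced but gives no dropout rate. This assumption favours the protocol.

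**Formula** (two-proportion z-test, pooled variance under the null)

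Power = Φ[(p2 − p1 − 1.96·SE0) / SE1], where SE0 = √(2·p̄(1−p̄)/n), SE1 = √((p1(1−p1) + p2(1−p2))/n) and p̄ = (p1+p2)/2.

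**Attempt to reproduce the stated figure: 5% vs 7%**
- p̄ = 0.06; SE0 = √(0.1128/500) = 0.01502; SE1 = √(0.1126/500) = 0.01501.
- (0.02 − 1.96 × 0.01502)/0.01501 = (0.02 − 0.02944)/0.01501 = −0.629.
- Power = Φ(−0.629) = **26.5%**, against the stated >97%.

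The observed difference must exceed about 2.9 points to reach significance, which is more than the 2-point effect itself.

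**Top of the stated range: 5% vs 10%**
- p̄ = 0.075; SE0 = √(0.13875/500) = 0.01666; SE1 = √(0.1375/500) = 0.01658.
- (0.05 − 1.96 × 0.01666)/0.01658 = 1.046.
- Power = Φ(1.046) = **85.2%**.

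**Across the range (500 per arm, control 5%)**

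| Experimental rate | Power |
|---|---|
| 6% | 10.3% |
| 7% | 26.5% |
| 8% | 48.6% |
| 9% | 69.9% |
| 9.6% | 80% |
| 10% | 85.2% |
| 11.7% | 97% |

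**Sample size for 5% vs 7%**

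n per arm = (1.96·√0.1128 + zβ·√0.1126)² / 0.02². For 97% power, zβ = 1.881: (0.6583 + 0.6311)²/0.0004 ≈ 4,157 per arm. For 80% power the same formula gives 2,213 per arm.

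**Does the choice of test matter?**

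| Method | 5% vs 7% | 5% vs 10% |
|---|---|---|
| Unpooled z | 26.5% | 85.4% |
| Arcsine | 26.7% | 86.1% |
| Chi-square, exact power | 26.2% | 85.8% |
| Fisher's exact | 22.4% | 83.2% |
| Continuity-corrected z | 22.3% | 82.3% |
| One-sided z | 37.7% | 91.4% |

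A log-rank calculation agrees: 60 events (25 + 35) with hazard ratio ln 0.93/ln 0.95 = 1.41 gives about 27%.

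**Other readings of a 2-point gap**
- 8% vs 10%, 500 per arm: 19.6%.
- A control rate of essentially zero vs 2%, 500 per arm: about 89%.
- 1,000 misread as the size of each arm, 5% vs 7%: 46.9%.
- One sample against a fixed 5%, 7% observed: 53.1% with n = 500 and 78.9% with n = 1,000.
- 5% and 7% taken as annual rates and compounded: 72.0% over 4 years, 80.0% over 5 and 89.4% over 7.

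None reaches 97%.

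**The case against.** The strongest counter-argument is that section 8.0 names no test and refers to scenarios it does not show, so the figure may come from a calculation other than the one above. Two candidates deserve a hearing.

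*A paired calculation.* Section 4.1 says assay results will be compared with the participants' own standard-of-care surveillance results, and section 7.0 describes monitoring that concordance. If 2% of patients had a cancer found only by cfDNA and none the reverse, the power of a McNemar-type test with 500 pairs is the chance of seeing enough discordant cases. This is 93.5% if 6 are needed, 97.2% if 5 and 99.0% if 4. The stated figure lies in that range and may have arisen this way. But that is a within-patient question. Section 8.0 compares the randomised cohorts, and section 4.4 assigns the sequencing tests to experimental-cohort samples.

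*Annual rates.* If 5% and 10% were yearly rates, compounded power would exceed 99.9% at 4 years. But section 8.0 puts the rates at the end of the study, and that scenario is a gain of 5 points a year, not one of at least 2.

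Reading 2% as a two-fold rise gives 5% vs 10%, hence 85%.

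So these readings may explain the figure without rescuing it for the stated design. Three points from the other side do stand. The assay-performance and patient-reported endpoints do not depend on this power figure. How a null result would in fact be read is a prediction. And any replacement figure should name its test and its assumption about loss.

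**Conclusion.** The power statement is wrong as written and must be corrected. For the effect it names, 500 per arm gives about 27% power, not more than 97%. At the best case in the protocol's own range it gives about 85%, and no rate between 5% and 10% reaches 97%.

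The figures rest on a two-sided two-proportion z-test at 0.05, a 5% control rate at the end of the study, and all 500 per arm analysed. Loss would lower them: with an illustrative 10% loss (450 per arm), 5% vs 7% falls to about 24% and 5% vs 10% to about 81%. Among the between-arm tests tried, none brings 5% vs 7% above 38%, even one-sided.

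**What to change.** Replace the power sentence in section 8.0, deleting the 97% figure and the claim about a 2-point increase. Suggested wording:

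> With 500 participants per arm, a 5% cumulative diagnosis rate in the control arm and a two-sided two-proportion z-test at the 0.05 level, the study has 80% power to detect an increase to 9.6%, 85% for an increase to 10% and 27% for an increase to 7%, assuming no loss to follow-up.

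Also:
- State the time horizon of the 5% rate (for example, years from randomisation) and its basis.
- If a loss rate is expected, give it and recompute. At 10% loss, the 9.6% scenario falls from 80% to about 76%.
- Say that a non-significant result would not exclude a 2-point gain. At 5% vs 7% the 95% confidence interval half-width is 1.96 × 0.01501 ≈ 2.9 points.
- If another model was intended, show it and confirm that it matches the randomised comparison.

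This is one paragraph, with no extra patients and no change in conduct; the cost is a less favourable stated power. If the sponsor regards 2 points as the gain the trial must be able to detect, rewording is not enough: 80% power would take about 2,213 per arm. That decision is the sponsor's, and it should be made with the correct figure in view.
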